### 5.2. Secondary Objectives

The secondary objectives of the study are to compare exenatide 5 µg twice daily and exenatide 10 µg twice daily versus each other and versus placebo with regards to:

- the proportion of patients achieving an HbA1c at endpoint of <7%, ≤6.5%, and <6.5%
- body weight
- fasting serum glucose (FSG)
- self-monitored blood glucose (SMBG) measurements before and 2 hours after the two main meals of the day
- fasting serum insulin concentrations
- the incidence and rate of hypoglycemia
- beta-cell function and insulin sensitivity as measured by homeostasis model assessments (HOMA-B, HOMA-S) ([Matthews et al. 1985](#))
- the proportion of patients discontinuing the study due to failure to maintain glycemic control
- safety and tolerability including reporting of adverse events, antibodies to exenatide, calcitonin, carcinoembryonic antigen (CEA), vital signs, electrocardiograms (ECGs), laboratory measurements, urinalysis, and pubertal assessment

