### 11.2. Statistical and Analytical Plans

#### 11.2.1. General Considerations

All of the data will be entered, verified, and archived at Amylin Pharmaceuticals, LLC or its delegate. All data listings, summaries, and analyses will be performed under the guidance and approval of the assigned statisticians. A detailed statistical analysis plan (SAP) will be developed before database lock. The full analysis set will use the intent-to-treat (ITT) principle and include the data from all randomized patients who received at least 1 dose of study drug.

Although, patients randomly assigned to placebo will be assigned to take the volume equivalent to 5 µg exenatide twice daily, or to take the volume equivalent to 10 µg exenatide twice daily, those patients will be combined into 1 group for analysis purposes.

Multiplicity adjustments for the primary analysis will be performed using Fisher Protected Testing procedure. No imputation of missing data will be performed with the exception of the last observation carried forward (LOCF) of post-baseline values in change from baseline to endpoint analyses. All tests of treatment effects will be conducted at a two-sided significance level of 0.05 unless otherwise stated.

Supportive analyses will be performed on the per-protocol analysis set. Per-protocol patients will be randomized to study drug, adhere to the inclusion/exclusion criteria, and have a Week 28 HbA1c measurement.

Any change to the data analysis methods described in the protocol will require an amendment ONLY if it affects the primary analysis. Any other change to the data analysis methods described in the protocol and the justification for making the change will be described in the SAP as well as the clinical study report.

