#### **11.2.8.4. Episodes of Hypoglycemia**

The distribution of hypoglycemic episodes and hypoglycemia incidence will be summarized by treatment. Hypoglycemia rate (adjusted for duration of exposure to study drug therapy) will be summarized by treatment. Similar reports will be created for daytime and nocturnal hypoglycemia episodes. A method of analysis to compare treatments will be described in the SAP.

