1.1.2 Secondary objectives

The secondary objectives are:

- To compare the effects of EBID to those of PBO, after up to 28 weeks of study drug treatment, in adolescents with type 2 diabetes, on the following:
 - Proportion of patients achieving HbA1c goals
 - Body weight

- Fasting serum glucose (FSG) concentrations
- Fasting serum insulin (FSI) concentrations
- Self-monitored blood glucose (SMBG) measurements before and 2 hours after the two main meals of the day
- Beta-cell function (HOMA-B) and insulin sensitivity (HOMA-S) as measured by homeostasis model assessments (HOMA)
- Proportion of patients discontinuing the study due to failure to maintain glycemic control
- To assess the safety and tolerability of up to 28 weeks of EBID treatment, in adolescents with type 2 diabetes, on the following:
 - Adverse events
 - Incidence and rate of hypoglycemia
 - Antibodies to exenatide
 - Laboratory measurements (including CEA and calcitonin concentrations)
 - Vital signs and physical examination including Tanner pubertal stage
 - Electrocardiograms (ECGs)

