3.6.6 Study periods

The following definitions will be used to assign data to the correct study period. For details on which data will be presented in outputs for each endpoint, refer to Section 4.2.

Pre-treatment period: defined as the period prior to the date of the first dose of randomized study medication. All data for patients who do not receive randomized study medication will be considered pre-treatment.

Treatment period: defined as the date of first dose of randomized study medication to date of the Week 28 visit, or the ED visit for patients who discontinue the study prior to Week 28.

Safety follow-up period: defined as the day after the Visit 11 (Week 28) visit, or the day after the ED visit for patients who discontinue the study prior to Visit 11 to the date of completion of the Safety follow-up study (typically after 3 years or once the patient has a height difference of less than 5 mm between two 6-month interval visits). The safety follow-up period will only be defined for patients who enter the safety follow-up period.

See Section 4.1.3 for details on missing data handling.

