4.2.5.2 Hypoglycemic episodes

Confirmed hypoglycemic episodes will be defined as follows:

Minor hypoglycemia:

- Any time a patient feels that he or she is experiencing a sign or symptom associated with hypoglycemia that is either self-treated by the patient or resolves on its own and
- Has a concurrent fingerstick blood glucose <3.0 mmol/L (54 mg/dL).

Major hypoglycemia:

- any episode with symptoms consistent with hypoglycemia resulting in loss of consciousness or seizure that shows prompt recovery in response to administration of glucagon or glucose or
- documented hypoglycemia (blood glucose <3.0 mmol/L [54 mg/dL]) requiring the assistance of another person because of severe impairment in consciousness or behavior (regardless of whether symptoms of hypoglycemia are detected by the patient).

Episodes will be categorized into major or minor following medical review of the hypoglycemic data by an AstraZeneca or IQVIA physician.

Incidence of hypoglycemic episodes will be summarized by whether they are major or minor and by when the episodes occurred (night-time will be defined to be between 11pm and 5 am) using frequencies and percentages of patients with at least one episode of hypoglycemia occurring during the study. The number of episodes per patient will be classified into categories (0, 1 to 2, 3 to 4, ≥ 5), and summarized using frequencies by treatment group and visit for the Safety analysis set.

Similar analyses will be performed for confirmed hypoglycemic episodes (those with a blood glucose record) and unconfirmed hypoglycemic episodes (those reported into study database without corroborating blood glucose record).

Minor and Major hypoglycemia rate (adjusted for duration of exposure to study drug therapy = the date of last dose of IP – date of first dose of IP +1) will be summarized by treatment.

The number and percentage of patients with any confirmed and unconfirmed hypoglycemic episodes will also be summarized by baseline sulfonylurea use (yes/no) and treatment.

Hypoglycemic events will be listed.

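### The SAP gives no method for the hypoglycemia comparison that the protocol promised and does not record its omission; the event window and the rate denominator also appear not to match

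*SAP*

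**What the plan says.** **Protocol.** Section 5.2 sets out to compare the two exenatide doses "twice daily versus each other and versus placebo with regards to" a list of outcomes that includes "the incidence and rate of hypoglycemia". Section 11.2.8.4 plans summaries of distribution, incidence and exposure-adjusted rate, then adds: "A method of analysis to compare treatments will be described in the SAP". Section 11.2.1 reserves amendments for changes to the primary analysis. For any other change of method, the change and "the justification for making the change will be described in the SAP as well as the clinical study report".

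**SAP, comparison.** Section 1.1.2 lists "Incidence and rate of hypoglycemia" under the objective of assessing safety and tolerability, not under the objective of comparing exenatide with placebo. Section 4.2.5.2 summarises incidence "using frequencies and percentages of patients with at least one episode of hypoglycemia occurring during the study", together with episode-count categories, a split by baseline sulfonylurea (SU) use and a listing. Section 6 mentions hypoglycemia only to say that the SU split is added to what the protocol specified.

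**SAP, rate.** Section 4.2.5.2 has a "Minor and Major hypoglycemia rate (adjusted for duration of exposure to study drug therapy", with exposure defined as last dose date minus first dose date plus 1, summarised by treatment. Section 3.4 defines hypoglycemic events over the treatment period. Section 3.6.6 reads "Treatment period: defined as the date of first dose of randomized study medication to date of the Week 28 visit, or the ED visit", the latter applying to anyone stopping early. Table 10 assigns episodes up to the last day of that period.

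**The concern.** The protocol left the comparison method to the SAP, and the SAP neither supplies one nor says that the comparison was abandoned. A reader of the study report would see percentages and rates side by side with no estimate of the difference and no measure of its uncertainty. Section 6 does record other departures: the GLMM, the per-protocol analysis, dose pooling, and the restriction of antibody data to listings. Its silence here therefore reads as if the protocol analysis had been kept.

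The rate raises a smaller question. If events are taken over the treatment period as the SAP defines it, the days between last dose and the ED visit can contribute episodes but no exposure. Any resulting overstatement would grow with the share of early discontinuers and the delay to their ED visits, and both may differ between arms.

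**Working it through.** **Step 1: the comparison.** Set side by side, the sections read as follows.

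| Question | Protocol | SAP |
|---|---|---|
| Is hypoglycemia to be compared? | Yes (5.2, 11.2.8.4) | Listed for assessment (1.1.2) |
| Is a method given? | Deferred to the SAP (11.2.8.4) | None (4.2.5.2) |
| Is a change recorded with its reason? | Required (11.2.1) | Not for this item (Section 6) |

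The pooling reason in SAP Section 6 is confined to efficacy analyses, so it does not cover this omission. Nor is all safety in the SAP descriptive. Section 4.2.5.4 gives change in eGFR a least squares mean difference, 95% CI and p-value, although Section 6 says the protocol does not specify eGFR as an endpoint.

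**Step 2: the two windows.** Events run from first dose to the Week 28 or ED visit (SAP 3.4, 3.6.6, Table 10). Person-time runs from first to last dose, both days included (4.2.5.2). A gap between last dose and the ED visit is foreseeable:
- SAP 4.2.5.1 provides for an ED visit after last dose.
- Protocol 6.1.6 asks patients to return as soon as possible but sets no limit.
- Protocol 7.4 discontinues patients who miss more than 10 consecutive days of study therapy.

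Completers omit only the morning injection at Visit 11 (Protocol 6.1.5). Their gap should be about a day or less and is left out below.

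**Step 3: size of the mismatch.** The documents give no hypoglycemia rate and no gap length, so there is no figure to reproduce. Let d be the share who discontinue, L their mean days on drug and g the gap in days. Completers have 28 × 7 = 196 days. Assume episodes occur at the same rate in the gap as on drug.

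Pooled overstatement = d·g / (d·L + (1 − d)·196)

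Take d = 0.23, the planning rate for the exenatide arms (Protocol 11.1), with assumed L = 98 or 28 and g = 7 to 30.
- L = 98: the denominator is 22.54 + 150.92 = 173.46. At g = 7, 1.61/173.46 = 0.9%. At g = 30, 6.90/173.46 = 4.0%.
- L = 28: the denominator is 6.44 + 150.92 = 157.36. At g = 7, 1.61/157.36 = 1.0%. At g = 30, 6.90/157.36 = 4.4%.

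Over d from 10% to 35%, the range is 0.4% to 7.7%.

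For one discontinuer the factor is (L + g)/L. It is 1.07 to 1.31 at L = 98, and 1.25 to 2.07 at L = 28.

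The SAP does not say whether the rate is pooled or a mean of per-patient rates. For a mean, the overstatement is d·g/L, assuming a common event rate. At d = 0.23 this runs from 0.23 × 7/98 = 1.6% to 0.23 × 30/28 = 24.6%.

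If discontinuation were 23% on exenatide and 10% on placebo, the pooled rate ratio would shift by about +0.5% to +2.7%. At 23% against 35%, it would shift by −0.6% to −3.0%.

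**Step 4: what a comparison could show.** SAP 1.3 gives 122 patients at 2:1, about 81 and 41. The documents state no incidence. With a common assumed incidence p, the 95% half-width is 1.96·√[p(1 − p)(1/81 + 1/41)]. This gives 8, 11 and 15 percentage points at p = 5%, 10% and 20%. At 10% against 5%, it is 1.96·√(0.09/81 + 0.0475/41) = 9.3 points, an interval of about −4 to +14. At 5%, only 0.05 × 41 ≈ 2 placebo patients would have an event, so these normal approximations are only a guide.

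**The case against.** The strongest reply is that safety data are usually described, not tested. The comparative wording in Protocol 5.2 also covers adverse events, ECGs, laboratory data and vital signs, which the protocol itself analyses descriptively. That stands: a reader might infer that section 5.2 alone demands inference, and it does not. The specific commitment is the sentence in 11.2.8.4. It is also true that the protocol could be satisfied without any new model, by a justified entry in SAP Section 6, and that no amendment is needed. There is no such entry.

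On the rate, a reader might infer that the SAP expressly counts events to the ED visit. It does not. The rate sentence is silent on its event window, and Table 10 may serve only to assign episodes to visits. The denominator itself follows the protocol's adjustment for exposure to study drug. A reader might also infer that rates for early discontinuers are bound to be too high. That holds only if episodes occur after last dose, and the documents give no off-drug rate. Where loss of glycemic control is confirmed by glucose, Protocol 6.1.7 makes the unscheduled visit the ED visit, so little gap is expected. What remains is that the SAP states no event window other than the treatment period, and nothing cuts episodes at last dose.

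Finally, stratified or count models may not be estimable with a handful of events. That is right, and it limits what the fix should ask for.

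**Conclusion.** The main point holds on the text alone. The protocol committed to a comparison with its method in the SAP; the SAP has no method and no record of the change. Following the plan leaves a secondary objective without a between-arm estimate. The primary analysis is unaffected.

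The rate point holds as a conditional and secondary matter. The pooled overstatement of about 1% to 4% rests on 23% discontinuation, a planning figure for the exenatide arms only; on assumed gaps of 7 to 30 days; and on an unchanged episode rate after last dose. With no episodes in the gap it is zero. It can be considerably larger for individual early stoppers, or if per-patient rates are averaged. This should be changed, but it does not threaten the trial's main conclusion.

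**What to change.** In SAP 4.2.5.2:
1. Add the incidence difference, Total EBID minus placebo, with an exact or score-type 95% CI, unstratified if the SU strata are sparse.
2. Add a rate ratio with 95% CI, using log exposure as offset, where event counts allow. Otherwise report descriptive rates only.
3. Count events for the rate from first dose through last dose inclusive, to match the existing denominator, or extend both by the same number of days. Adding one day to the event window alone would leave a mismatch of 1/196, about 0.5%, in every completer.
4. State whether the rate is pooled or averaged over patients, and its unit.

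In SAP Section 6, record with the reason any part of the protocol comparison not done, including the comparison between doses.

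The cost is a paragraph and one table, from data already collected. The downside is wide intervals if events are rare.

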4.2.5.3 Antibodies to exenatide

A patient is said to have treatment emergent antibodies to exenatide at a visit if the antibody test is positive after the first injection of study medication following a negative or missing antibody measurement prior to the first injection of study medication, or the titer is increased by at least 3 dilutions from a detectable measurement prior to the first injection of study medication.

Patients with antibodies to exenatide during the treatment, as well as incidence of negative, any positive, low positive (<625), and high positive (≥ 625) will also be summarized descriptively by visit.

4.2.5.4 Laboratory data (including CEA and calcitonin concentrations)

Continuous laboratory parameters will be summarized in standardized international (SI) and US units. The visit windows described in Section 4.3.2 will be used. There will be no imputation for missing values.

All hematology, clinical chemistry and urinalysis results will be listed by treatment group, patient, and visit, including scheduled and unscheduled/repeat measurements. Laboratory assessments that are outside of normal ranges will be flagged. Separate listings of laboratory values above/below the upper/lower limit of the reference range will be produced. The central laboratory or local laboratory (for assessments measured at a local laboratory) reference ranges will be used. The observed values at each visit to Visit 11 (Week 28) and change from baseline values will be summarized for each of the quantitative laboratory assessments by treatment group for the Safety analysis set. For categorical parameters, shift tables from baseline to each visit to Visit 11 (Week 28) will be produced by treatment group for the Safety analysis set. Tumor marker CEA and calcitonin levels will also be summarized by visit for the Safety follow-

up analysis set. These summaries will include observed values at each visit from Visit 3 (Week 0) through Visit 11 (Week 28) to end of the safety follow-up period and change from baseline by actual treatment group during the randomized period and overall.

Number and percentage of laboratory results that are potentially clinically significant (see Appendix 6) will be listed and summarized by analyte name and criteria for each treatment group for the safety analysis set. A listing of calcitonin values >100 ng/L will be produced.

Estimated glomerular filtration rate (eGFR) will be derived based using the Bedside Schwartz formula (Schwartz, 2009):

$$\text{eGFR} = 41.3 * (\text{Height in meters} / \text{Serum creatinine in mg/dL})$$

A table of observed and change from baseline in eGFR values will be provided. This will be provided both overall and by baseline eGFR, hyperfiltrating versus non-hyperfiltrating, where hyperfiltration is defined as an eGFR ≥ 125 ml/min/1.73m².

An ANCOVA analysis of change in eGFR from baseline to Week 28 by baseline eGFR (hyperfiltrating: ≥ 125 ml/min/1.73m² versus non-hyperfiltrating: < 125 ml/min/1.73m²) will be provided. The same multiple imputation approach as stated in Section 4.2.4.4 will be used. The model will include treatment, screening HbA1c strata ($\leq 8\%$, $> 8\%$), background diabetes therapy strata (drug naïve, metformin only, SU only, and metformin + SU), baseline eGFR as the fixed effects. The least squares mean, 2-sided 95% confidence interval, and p-value of the difference in the endpoints of interests between Total EBID and PBO groups will be presented. This analysis will be done both excluding data after initiation of rescue therapy and separately including data after initiation of rescue therapy.

eGFR will also be calculated using the Chronic Kidney Disease Epidemiology Collaboration (CKD-EPI) formula (Levey et al, 2009):

$$\text{eGFR} = 141 \times \min(\text{Scr}/\kappa, 1)^\alpha \times \max(\text{Scr}/\kappa, 1)^{-1.209} \times 0.993^{\text{Age}} \times [1.018 \text{ if female, } \times 1.159 \text{ if black}]$$

where Scr is serum creatinine, κ is 0.7 for females and 0.9 for males, α is -0.329 for females and -0.411 for males, min indicates the minimum of Scr/ κ or 1, and max indicates the maximum of Scr/ κ or 1.

eGFR using the CKD-EPI equation will be summarized at baseline and may be analyzed as a sensitivity analysis.

Strip Sign for Selected Laboratory Data

For selected laboratory test values that have been received with a qualifier as a part of the result ($>$, \geq , $<$, or \leq), a process to strip the qualifier will be applied and the resulting numeric values will be used for data analysis. The raw value with operator will remain as such in the database and will be used when listed.

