The main risks associated with exenatide treatment include mild or moderate nausea (for approximately half of treated patients) that is more frequent at the initiation of therapy and an increased risk of mild or moderate hypoglycemia if the patient is also using an SU. Approximately 43% of adult patients taking exenatide exhibit a temporal rise in antibodies to exenatide, which are mostly of low titer ( $< 1/125$ ). In about 3% of all patients in the three 30-week registration trials, the formation of antibodies to exenatide at high titers was associated with failure to achieve adequate improvement in glycemic control. Postmarketing reports have linked exenatide use to acute pancreatitis and to altered renal function. As it is eliminated by the kidneys, exenatide should not be used by patients with severe renal impairment or end-stage renal disease.

Type 2 diabetes accounts for approximately 45% of all new cases of diabetes in adolescents (Dietz and Robinson 2005). Evidence has shown that a diagnosis of type 2 diabetes in childhood, coupled with inadequate glycemic control, increases the risk of early mortality as well as early end organ damage (Cavallo 2006). The current study will investigate the safety and efficacy of exenatide in the treatment of type 2 diabetes in adolescents, and will provide important information on the potential clinical use of exenatide in that population.

More detailed information about the known benefits and risks of exenatide may be found in the Investigator's Brochure (IB).

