4.2.5.5 Vital signs

Vital signs (systolic and diastolic blood pressure and heart rate) will be summarized by visit and treatment group for the safety analysis set. Observed and change from baseline values will be summarized for each visit where appropriate. This summary will be repeated by age group (< 12 years, ≥ 12 years).

Number and percentage of vital signs that are potentially clinically significant (see [Appendix 7](#)) will be summarized by parameter, category, treatment group and age group (<12 years, ≥12 years). Individual patient data for patients with marked abnormality criteria will be listed.

Vital signs parameters will be listed.

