4.3.2 Visit assignment for safety variables

Table 7 Visit Windows: Antibodies to exenatide and vital signs

Visit	Week	Period	Target Day	Day range
3	0	TP	1	Baseline
5	4	TP	29	2-56
7	12	TP	85	57-112
9	20	TP	141	113-168
11	28	TP	197	169-last day of TP

TP: Treatment period.

Table 8 Visit Windows: Body weight, height, BMI and Tanner pubertal assessment

Visit	Week	Period	Target Day	Day range
3	0	TP	1	Baseline
5	4	TP	29	2-56
7	12	TP	85	57-112
9	20	TP	141	113-168
11	28	TP	197	169-last day of TP
801	+26	SFU	+183	last day of TP+1-273
802	+52	SFU	[contact]	+78	SFU	[contact]	+104	SFU	[contact]	+130	SFU	[contact]/ED	+156	SFU	+1093	1002-last day of SFU

TP: Treatment period. SFU: Safety follow-up period (+ denotes relative to Visit 11/ED)

Table 9 Visit Windows: Laboratory data, ECG, waist circumference and hip circumference

Visit	Week	Period	Target Day	Day range
3	0	TP	1	Baseline
11	28	TP	197	2-last day of TP
801	+26	SFU	+183	last day of TP+1-273
802	+52	SFU	[contact]	+78	SFU	[contact]	+104	SFU	[contact]	+130	SFU	[contact]/ED	+156	SFU	+1093	1002-last day of SFU

TP: Treatment period. SFU: Safety follow-up period (+ denotes relative to Visit 11/ED). Only CEA and calcitonin measured during SFU

Table 10 Visit windows: Hypoglycemic episodes

Visit	Week	Period	Target Day	Day range
3	0	TP	1	Baseline
4	2	TP	15	2-21
5	4	TP	29	22-42
6	8	TP	57	43-70
7	12	TP	85	71-98
8	16	TP	113	99-126
9	20	TP	141	127-154
10	24	TP	169	155-182
11	28	TP	197	183-last day of TP

TP: Treatment period.

Collected at clinic visits but discussed during telephone visits

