4.3.3 Rules for safety observations

4.3.3.1 Multiple safety assessments

The assessments for laboratory parameters will be based only on central laboratory values if results for both local and central labs exist.

For the baseline visit window see section 3.6.1. For other visit windows rules below apply.

For laboratory efficacy parameters, if a patient has more than one measurement (scheduled or unscheduled) included within a relative day window, the assessment closest to the target day and time (the target time is always assumed to be 8:00 am) will be used. In case of ties between observations located on different sides of the target day and time, the later assessment will be used. In case of ties located on the same side of the target day and time (i.e. more than 1 value for the same day and time), the mean of the values will be used.

For non-laboratory efficacy parameters, if a patient has more than one measurement (scheduled or unscheduled) included within a relative day window, the assessment closest to the target day will be used. In case of ties between observations located on different sides of the target day, the later assessment will be used. In case of ties located on the same side of the target day (i.e., more than 1 value for the same day), the mean of the values will be used.

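### The tables of potentially clinically significant laboratory and vital-sign values count results rather than patients, and name no denominator or value-selection rule

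*SAP*

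**What the plan says.** **Unit.** SAP 4.2.5.4 tabulates the "Number and percentage of laboratory results that are potentially clinically significant" against the Appendix 6 limits. These "will be listed and summarized by analyte name and criteria for each treatment group for the safety analysis set". There is no visit dimension. SAP 4.2.5.5 has the parallel sentence, "Number and percentage of vital signs that are potentially clinically significant", against Appendix 7, split by parameter, category, arm and age group. Neither sentence names a denominator or says which of several values is used.

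**Default.** SAP 4.1.1 summarizes categorical variables as patients, with percentages out of the analysis-set total unless stated otherwise. Protocol 11.2.8.3 plans the proportion of patients outside the reference range at the final visit. SAP section 6 lists no change of unit.

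**Windows.** The paragraph of SAP 4.2.5.4 on continuous parameters says "The visit windows described in Section 4.3.2 will be used". In Table 9 the only treatment-period laboratory window after baseline runs "2-last day of TP", with target Day 197. Table 7 gives vital signs four post-baseline windows (Weeks 4, 12, 20 and 28).

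**Several values in one window.** SAP 4.3.3.1 is headed as a rule for safety assessments but begins "For laboratory efficacy parameters, if a patient has more than one measurement (scheduled or unscheduled) included within a relative day window" and then keeps the value nearest the target. No other rule is written for safety laboratory values.

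**Schedule.** In protocol Attachment 1, chemistry after baseline is drawn only at Visit 11 or early discontinuation. Blood pressure and heart rate are taken at Visits 5, 7, 9 and 11.

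**The concern.** A table of marked abnormalities is read as the share of patients in each arm who had one. A table of results does not give that share. Its percentage moves with how often each patient was measured, and it cannot separate one patient with repeated abnormal values from several patients with one each.

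The laboratory table has a second open question, namely which values enter it. A creatinine, ALT or AST value between baseline and the end of treatment can only come from an unscheduled, repeat or off-schedule draw, so the treatment of such values decides what the table shows. Renal findings matter for this drug. Protocol 4.1 states: "Postmarketing reports have linked exenatide use to acute pancreatitis and to altered renal function". The current SAP text has no other laboratory table built on any-time or worst on-treatment values.

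**Working it through.** The plan states no figure to reproduce. The check applies each permitted reading to the same data. All patient data below are hypothetical.

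**1. Laboratory: the two readings give different answers.** Take the Appendix 6 ALT limit (above 3 × ULN). Four patients have seven post-baseline values, in multiples of ULN:

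| Patient | Values (day) | Any value above 3 | Value nearest Day 197 |
|---|---|---|---|
| A | 5.0 (60), 3.4 (74), 0.9 (197) | yes | 0.9 |
| B | 0.9 (197) | no | 0.9 |
| C | 4.0 (90, early discontinuation) | yes | 4.0 |
| D | 4.0 (190), 0.9 (200) | yes | 0.9 |

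- Patients ever above the limit: 3/4.
- All records counted: 4/7 results. Patient A counts twice.
- Table 9 window with the nearest-value rule: 1/4. A and D drop out because their peaks recovered. C stays because that is the only value in the window.

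Under the windowed reading each patient has one post-baseline value per analyte, so results equal patients. Under the all-records reading the peaks are tabulated. Repeat counting and a lost peak are therefore alternatives.

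**2. Laboratory: possible size.** Two thirds of the 122 randomized patients is 122 × 2/3 ≈ 81 on exenatide. Assume all 81 are treated, each with one normal end-of-treatment value, plus five flagged unscheduled values in total. The number of results is 81 + 5 = 86.

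| Who produced the five flagged values | Patient rate | All records, over results | All records, over the safety set (4.1.1 denominator) | Windowed |
|---|---|---|---|---|
| Five patients, one each | 5/81 = 6.2% | 5/86 = 5.8% | 5/81 = 6.2% | 0/81 = 0% |
| One patient, five repeats | 1/81 = 1.2% | 5/86 = 5.8% | 5/81 = 6.2% | 0/81 = 0% |

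No reading that follows the stated unit separates the two rows.

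**3. Vital signs: no unscheduled visit is needed.** Four scheduled post-baseline measurements in 81 patients give 4 × 81 = 324 results per parameter. Four flagged results are 4/324 = 1.2% over results, or 4/81 = 4.9% over the safety set. Both hold whether one patient was flagged four times (patient rate 1/81 = 1.2%) or four patients once each (4/81 = 4.9%). Here windowing and repeat counting operate together.

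**4. Baseline values.** SAP 2.1.5 and 3.6.6 tie safety summaries to a period starting on the date of first randomized dose, which excludes screening values. A Visit 3 sample taken that day still falls inside the period by date, although SAP 3.6.1 treats it as baseline. Neither sentence excludes it.

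**The case against.** **The general rule already says patients.** SAP 4.1.1 could be read as governing these tables, leaving one loose word. Part of this stands: a careful programmer might count patients. But the specific sentences name a different unit, and elsewhere the SAP writes patients when it means them (adverse events, hypoglycemia, ECG). Applying only the 4.1.1 denominator to a count of results gives the 6.2% for one patient shown above.

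**Windowing of the laboratory table is not written.** This stands. The windows sentence belongs to the paragraph on continuous parameters, the Appendix 6 sentence cites no window, and the nearest-value rule is worded for efficacy parameters. A reader might infer that the SAP definitely discards every value except the one nearest Day 197, or that the laboratory table both counts patients repeatedly and loses peaks. The documents support neither inference.

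**A recovered peak would be seen elsewhere.** Largely right. SAP 4.2.5.4 lists all results, including unscheduled and repeat ones, with separate out-of-range listings. Under protocol 9.2.1 a clinically significant laboratory finding that results in a diagnosis goes on the adverse event page, and so reaches tables by arm. What is missing is a by-arm patient rate for peaks that led to no diagnosis.

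**The protocol looked only at the final visit, and the schedule is the larger limit.** Both true. The protocol did not promise a worst-value table. The eGFR endpoint is defined at Week 28, so leaving out a mid-treatment value there is not an error. With no scheduled mid-treatment chemistry, no analysis can recover peaks that were never sampled. Neither point settles the unit, and the protocol's own unit is patients.

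**Any-time rates from unscheduled tests can be biased.** This stands. Protocol 4.1 reports nausea in about half of treated patients, so symptom-driven testing could differ by arm even under blinding.

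**Conclusion.** The concern holds as a fault of unit and definition. As written, the two tables do not give the proportion of patients affected by arm, and they depart from SAP 4.1.1 and protocol 11.2.8.3 without saying so.

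For vital signs this follows from the schedule alone: up to four counts per patient per parameter. For laboratory data the effect depends on which reading is adopted and on an unknown number of unscheduled tests. The 6.2%, 5.8% and 1.2% figures illustrate the mechanism and do not estimate what the trial will show. They assume 81 treated exenatide patients with one end-of-treatment value each and five flagged unscheduled values.

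The primary efficacy analysis, power and type I error are unaffected. The documents do not support a claim that laboratory toxicity would go unreported.

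**What to change.** In SAP 4.2.5.4 and 4.2.5.5, replace the unit with: the number and percentage of patients with at least one post-baseline value during the treatment period meeting each Appendix 6 or Appendix 7 criterion. Specify that:

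- all scheduled and unscheduled values are used, without windowing;
- each patient counts once per parameter and criterion;
- the denominator is safety-set patients with at least one post-baseline value, and also a baseline value for criteria based on change.

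Beside this, show the rate from scheduled Week 28 or early-discontinuation values only, so that any difference between arms in symptom-driven testing can be judged.

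In SAP 4.3.3.1, limit the nearest-to-target rule to by-visit summaries and correct its efficacy wording so that its scope is clear. State whether a locally analysed unscheduled value counts, since the same section uses central values only where both exist. Record the change in SAP section 6.

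The cost is a few sentences and a small programming change on data already collected. No visit, sample or clinical rule changes. The price is that any-time rates will tend to be higher than final-visit rates and will partly reflect who was retested; the report should say so.
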